8.2.2. Serum Biomarkers

Biomarkers of liver inflammation and fibrosis will be presented, including autotaxin, ProC3, hsCRP, MMP7, MMP9, ELF score, and CA 19-9. ELF individual factors (Procollagen 3, Hyaluronic Acid (HA), Tissue Inhibitor of Metalloproteinase 1 (TIMP1)) will be displayed along with ELF score. Bile acid synthesis biomarkers, C4 and FGF-19, will also be assessed. Relative and absolute change from baseline 1 for the serum biomarkers will be presented according to [Table 2](#). Baseline 1 is defined as assessment performed on the day of the planned single dose.

Similar summary tables presenting relative and absolute change from baseline 2 for the 12-week treatment period will be presented for all above serum biomarker parameters for patients in the PD analysis set who actively entered the 12-Week treatment period. Baseline 2 for the 12-week treatment period is defined as the last non-missing value of the assessment prior to the 12-week treatment period (V3).

A listing of serum biomarker parameters will be presented for the PD analysis set.

9. Safety Analysis

Safety will be assessed through summaries of TEAEs, serious adverse events (SAEs), vital signs, ECGs, physical examinations, clinical laboratory tests (hematology, clinical chemistry, urinalysis, and coagulation), and concomitant medication. Analyses will be performed using the Safety Analysis Set.

9.1. Adverse Events

An AE is defined as any untoward medical occurrence in an enrolled patient regardless of causal relationship with the study drug. An AE can therefore be any clinically significant unfavorable and unintended sign, symptom, or disease that occurs during the study, whether or not related to the study drug.

A TEAE in this study is defined as an AE occurring during the treatment period and within 14 days follow-up after the last dose that meets any of the following conditions:

- Any new AE that occurs on or after the first dose of study drug;
- An existing disease that occurs before the first dose of study drug, but worsens in severity on or after the first dose of study drug.

Adverse events will be coded using Version 28.0 of the MedDRA. The severity of AEs will be assessed by the investigator based on the Common Terminology Criteria for Adverse Events (CTCAE), Version 5.0 grading system.

Summary of AEs will include.

- Overview of the incidence of TEAEs (TEAEs, TEAEs by Severity, Serious TEAEs, Drug-related TEAEs, Serious Drug-related TEAEs, Severe Drug-Related TEAEs, TEAEs leading to treatment discontinuation, Drug-related TEAEs leading to treatment discontinuation, TEAEs leading to treatment interruption, Drug-related TEAEs leading to treatment interruption, TEAEs leading to study discontinuation, Drug-related TEAEs leading to study discontinuation, and TEAEs leading to death).
- TEAEs by SOC and PT.
- TEAEs by PT in Descending order of frequency.
- TEAEs by Severity, SOC and PT.
- Study Drug-related TEAEs by SOC and PT.
- Study Drug-related TEAEs by PT in Descending order of frequency.
- Study Drug-related TEAEs by Severity, SOC and PT.
- TEAEs leading to treatment discontinuation by SOC and PT.
- Study Drug-related TEAEs leading to treatment discontinuation by SOC and PT.
- TEAEs leading to treatment interruption by SOC and PT.
- Study Drug-related TEAEs leading to treatment interruption by SOC and PT.
- TEAEs leading to study discontinuation by SOC and PT.
- Study Drug-related TEAEs leading to study discontinuation by SOC and PT.
- Serious TEAEs by SOC and PT.

A patient with multiple AEs within a primary SOC or PT will only be counted once towards the total for that SOC and/or PT. For the AE severity and relationship summaries, if a patient reported more than one AE with the same PT, the AE with the greatest severity or relationship will be presented. For table summaries if severity is missing then 'Grade 3 (Severe)' is assumed. For the purposes of summarising AEs related to study drug, a relationship of 'possibly related', 'probably related' or 'definitely related' will be considered as related to the study drug. A relationship of 'not related' or 'unlikely related' will be considered as not related to the study drug. If relationship is missing, relationship to study drug is assumed to be 'related'. AEs with a

toxicity grade of greater than or equal to grade 3 will be considered as severe adverse events. Summaries of TEAEs will be presented separately by the single dose (Day 1 to Day 14), 12-week (Day 15 to Day 112) and overall treatment periods by treatment arm and overall.

Following patient listings will be provided based on the safety analysis set.

- TEAEs
- SAEs
- Drug-related AEs
- AEs leading to treatment discontinuation
- AEs leading to treatment interruption
- AEs leading to study discontinuation
- Deaths

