Study data will also be reviewed by the SRC at regularly scheduled meetings, as described in the SRC charter. The SRC will also convene ad-hoc meetings as necessary. The SRC will also review an optional interim analysis that may be completed when the last patient in any arm has reached 4 weeks of treatment.

There will be a total of 8 scheduled visits during the study (including 1 Screening Visit).

Patients not meeting eligibility criteria may be re-screened once, after consultation with the medical monitor. Laboratory values that are within the inclusion and exclusion criteria are to be repeated to determine if the patient can enter the treatment period. Patients not fulfilling inclusion/exclusion criteria thereafter will not be allowed into the study.

Figure 1: Study Design

*EASL defined MRCP Equivalent of clinically relevant strictures: A biliary stricture on MRI/MRCP with > 75% reduction of duct diameter in the common bile duct or hepatic ducts

BID = twice daily; f/u = follow up; PK = pharmacokinetic; QD = once daily; wks = weeks

Patients will be instructed on the daily use of a Patient Diary. The Patient Diary will include NRSs for evaluation of pruritus (only patients with pruritus at the Screening Visit), fatigue, and sleep disturbance (see [Appendix 1](#)), and a Likert scale to assess mood throughout the study. Additionally, patients will be requested to use the Patient Diary to report study drug administration during the Treatment Period. Patient Diaries will be collected at each study visit and the next diary distributed.

The last dose of study drug will be administered at Week 12 (Visit 7) and the End-of-Study Visit (Visit 8) will take place 14 days later. Patients who prematurely discontinue from the study for any reason will undergo End-of-Treatment procedures at the time of discontinuation and End-of-Study procedures within 14 days after the last dose of study drug. With the exception of patients that discontinue due to an adverse event, withdrawn or terminated early patients may be replaced, as needed, to ensure 6 patients are enrolled into the 12-week Treatment Period of each treatment arm. The end of the study is defined as the time when the last patient completes their last visit.

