2.1. Primary Objective

To evaluate the safety and tolerability of A3907 in patients with PSC with and without a Clinically Relevant Strictures (CRS) following repeat doses.

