3.2. Study Endpoints

3.2.1. Primary Endpoints

The primary endpoint is safety and tolerability as determined by the incidence of treatment-emergent adverse events (TEAEs) through Week 12.

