displayed to two levels of precision greater than the data collected up to a maximum of three decimal places. A row denoted “Missing” will be included in count tabulations where specified on the shells to account for dropouts and missing values. The denominator for all percentages will be the number of patients in that treatment arm within the population of interest, unless otherwise specified. Refer to the [Appendix 1](#) for imputation rules for partial and missing AE onset dates as well as partial and missing prior/concomitant medication start and end dates. Data will be displayed in all listings sorted by treatment arm.

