4.1. Sample Size

Due to the exploratory nature of this study, no formal power calculations will be used to determine sample size. Approximately 24 patients will be enrolled with six (6) patients in each treatment arm. To ensure 6 patients are enrolled into the 12-week Treatment Period of each treatment arm, patients that discontinue due to an adverse event, withdrawn or terminated early patients may be replaced as needed.

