7.3. Study Treatments

7.3.1. Extent of Exposure

Treatment Exposure will be displayed by the single dose (Day 1 to Day 14) and 12-week (Day 15 to Day 112) treatment periods. For single dosing period, number of patients who received the single dose will be presented based on the Safety Analysis Set. Duration of 12-week treatment period exposure is defined as the total number of days a patient is exposed to the study drug during the 12-week treatment period. Duration of 12-week treatment period exposure will be presented as the total number of days from the first dose date and time in the 12-week treatment period to the last dose date and time (date of last known study drug administration minus the date and time of first dose in the 12-week treatment period + 1) as recorded on the End of Treatment electronic case report form (eCRF). If the last dose date and time on the End of Treatment page is missing, then the last dose date and time recorded on the A3907 Administration page of eCRF will be used. Duration of 12-week treatment period will be categorized into time intervals and frequency counts and percentages will be presented for the number (%) of patients in each interval. The time intervals will be grouped into the following categories: 1 to 14 days, > 14 to ≤ 28 days, > 28 to ≤ 42 days, > 42 to ≤ 70 days, > 70 to ≤ 98 days, and > 98 days. Duration of exposure will also be summarised using descriptive statistics. For 12-week treatment period summary, percentages will be computed from the number of patients in the Safety Analysis Set who actively entered 12-Week treatment period. All doses will be included in the listing based on the Safety Analysis Set.

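### By default the 12-week TEAE tables count patients who received only the single dose, and their fixed day limits do not follow actual dosing

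*SAP*

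**What the plan says.** **Tables and analysis set.** SAP Section 9 runs the safety analyses on the Safety Analysis Set, for which one dose is enough (SAP 4.3.3). SAP 9.1 states: "Summaries of TEAEs will be presented separately by the single dose (Day 1 to Day 14), 12-week (Day 15 to Day 112) and overall". It gives no denominator for any of the three periods. SAP Section 4 supplies the default: "The denominator for all percentages will be the number of patients in that treatment arm within the population of interest, unless otherwise specified".

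**Restriction used elsewhere.** For exposure in the 12-week period, SAP 7.3.1 says "percentages will be computed from the number of patients in the Safety Analysis Set who actively entered 12-Week treatment period". The same restriction to patients who entered the period appears for bile acids (8.2.1), serum biomarkers (8.2.2), laboratory data (9.2), MELD (9.7), FibroScan (9.9) and Mayo score (9.10).

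**Objective and endpoint.** The primary objective concerns safety "in patients with PSC with and without a Clinically Relevant Strictures (CRS) following repeat doses". The primary endpoint is "safety and tolerability as determined by the incidence of treatment-emergent adverse events (TEAEs) through Week 12".

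**TEAE window.** SAP 9.1: "A TEAE in this study is defined as an AE occurring during the treatment period and within 14 days follow-up after the last dose".

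**Stopping after the single dose.** A patient whose exposure after the single dose is above the limit is terminated early (SAP 3.3.1; Protocol 5.4 and 8.2). Footnote b of the protocol's Table 1 plans an End-of-Study Visit for these patients. Stopped patients may be replaced so that 6 per arm enter the 12-week period (SAP 3.1; Protocol 7.1.1).

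**Replacement after an adverse event.** Protocol 7.1.1 says "With the exception of patients that discontinue due to an adverse event, withdrawn or terminated early patients may be replaced", and SAP 3.1 keeps that exception. SAP 4.1 says "patients that discontinue due to an adverse event, withdrawn or terminated early patients may be replaced as needed". Protocol 7.2.4.2 allows withdrawn patients to be replaced and mentions no exception.

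**The concern.** The 12-week TEAE tables are the ones that isolate repeat dosing, which is what the primary objective asks about. A patient who received only the single dose cannot contribute a repeat-dose event. If such patients stay in the denominator, every percentage in those tables falls. If their number differs between arms, comparisons between arms are distorted as well. The design creates this group on purpose, through the exposure check after the single dose. Confirmation of stable ALP, which uses the Visit 2 value (Protocol 7.2.2, criterion 5), is a second possible route.

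The periods are also set by study day, not by the patient's own doses. Both ends of the 12-week period depend on visits with a window of ±2 days, so events near the limits can fall in the wrong table or in neither.

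**Working it through.** **Plan's own figure.** 4 arms × 6 patients = 24, as stated. There is no power calculation to reproduce.

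**1. Denominator.** Let k be the number of patients in an arm who received the single dose but never entered the 12-week period. The documents give no value, so k is an assumption. With 6 entrants, and no 12-week event recorded for a non-entrant:

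reported percentage = percentage among entrants × 6/(6+k)

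| k | Denominator | Factor | 3 patients with event | 1 patient with event |
|---|---|---|---|---|
| 0 | 6 | 1.00 | 50.0% | 16.7% |
| 1 | 7 | 0.86 | 42.9% | 14.3% |
| 2 | 8 | 0.75 | 37.5% | 12.5% |
| 3 | 9 | 0.67 | 33.3% | 11.1% |

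**2. Renumbering.** SAP Section 11 changes Day 0 to Day 1, so from dosing onward SAP day = protocol day + 1. Protocol 10.2.2.5 uses Day 0–13 and Day 14–112. Shifted, these become Day 1–14 and Day 15–113. The SAP prints Day 15–112. The 12-week period thus shrinks from 112 − 14 + 1 = 99 days to 112 − 15 + 1 = 98. In SAP Table 2 the FibroScan target days are 15, 43, 99 and 113, which are the shifted values.

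**3. Start of the 12-week period.** Visit 3 is protocol Day 14 ± 2, which is SAP Day 13–17. The SAP cut lies between Day 14 and Day 15.

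| Visit 3 (SAP day) | Repeat-dose days filed as single-dose | Days before repeat dosing filed as 12-week |
|---|---|---|
| 13 | 2 | 0 |
| 14 | 1 | 0 |
| 15 (on schedule) | 0 | 0 |
| 16 | 0 | 1 |
| 17 | 0 | 2 |

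**4. End of the 12-week period.** Visit 7, with the last dose, is protocol Day 98 ± 2, which is SAP Day 97–101. TEAE follow-up ends 14 days later.

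| Last dose (SAP day) | Last TEAE day | Days after Day 112 |
|---|---|---|
| 97 | 111 | 0 |
| 98 | 112 | 0 |
| 99 (on schedule) | 113 | 1 |
| 100 | 114 | 2 |
| 101 | 115 | 3 |

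Events after Day 112 are TEAEs by definition but belong to neither period table.

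**5. Non-entrants.** After a single dose on Day 1 the TEAE window ends on Day 1 + 14 = Day 15. An event on that day enters the 12-week table although the patient had no repeat dose. The denominator and the period limits should therefore change together. Otherwise a patient outside the new denominator could still be in the numerator.

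**The case against.** The strongest reply is that little depends on these tables. The study is descriptive, no decision rule uses the percentages, and the stopping rules in Protocol 7.2.4.3 count patients with related events. Counts are shown beside percentages, and TEAEs are listed by patient. This stands. It limits the consequence but does not make the denominator right.

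Second, the denominator is inferred. SAP 9.1 states none, the general rule speaks of a population of interest, and the table shells are not available. The cholangitis and dilation summaries (SAP 9.6 and 9.8) also cover the 12-week period without a restriction, so practice is not uniform. Even so, the SAP states the restriction wherever it reports exposure, PD or laboratory results for that period, and silence in 9.1 triggers the default.

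Third, the day ranges may be labels only. SAP 4.4 describes the period as Visit 3 to Visit 7, and SAP 7.3.1 prints the same range but computes exposure from actual dates. That is possible, but 9.1 gives no rule other than the days.

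A reader might infer three stronger points that the documents do not support:

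- *That the 12-week table carries the primary endpoint.* No table is named for it. The overall-period table also covers TEAEs through Week 12, and there the full Safety Analysis Set is the right denominator. The 12-week table itself runs past Week 12 into follow-up.
- *That the highest-dose arm is diluted most.* The exposure limits and supporting figures are redacted, so the chance of failing the check cannot be judged by arm.
- *That replacing patients who stop for an adverse event dilutes incidence.* A patient who entered the 12-week period and the replacement who also enters have both had repeat doses, and both belong in the denominator. A patient who stops after the single dose is already counted in k.

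**Conclusion.** The point holds as a gap in the specification of the 12-week TEAE tables. As written, patients with no repeat dose count in the denominator. One such patient beside 6 entrants lowers every percentage by a seventh in relative terms (50% to 42.9%), two by a quarter and three by a third. This rests on the SAP's default rule and on an assumed k. If every dosed patient enters the 12-week period, there is no effect.

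The period limits are a smaller, separate defect. Read literally, they lose 1 day for an on-schedule patient and 0 to 3 days within the visit windows. They misfile at most 2 days at the start if visits stay in window.

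The overall-period table is affected by neither problem, so TEAE incidence from first dose is still reported properly. The replacement rules for patients who stop for an adverse event contradict each other, and SAP Section 11 lists no change on this. That is an inconsistency, not a source of dilution.

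**What to change.** In SAP 9.1:

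1. For the 12-week TEAE tables, state that the denominator is the Safety Analysis Set patients who entered the 12-week period, as in SAP 7.3.1. Keep the full Safety Analysis Set for the single-dose and overall tables.
2. Define the periods by each patient's dosing. Single-dose: from the first dose to just before the first 12-week dose, or to first dose + 14 days if dosing never restarts. 12-week: from its first dose to last dose + 14 days. This also removes the Day 112 error. SAP Appendix 3 already anchors the diary weeks to the patient's own first day of 12-week treatment.

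Separately, SAP 4.1, SAP 3.1, Protocol 7.1.1 and Protocol 7.2.4.2 must be reconciled on whether patients who stop for an adverse event may be replaced.

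The cost is SAP wording and minor programming before the analysis is run. Some 12-week percentages will look less favourable.

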9.2. Clinical Laboratory Evaluations

Clinical safety laboratory evaluations will be performed by a central laboratory. Samples will be collected for clinical laboratory evaluations at timepoints indicated in [Table 1](#) and [Table 2](#). Safety lab parameter like clinical chemistry and urinalysis ([Appendix 2](#)) will be presented from Baseline up to Follow-Up after 12-Week Treatment. Hematology will be presented at Baseline, Start of 12-Week Treatment up to Follow-Up after 12-Week Treatment. Coagulation will be presented at Baseline, Start of 12-Week Treatment, Week 4 of 12-Week Treatment and Week 12 of 12-Week Treatment.

Descriptive statistics for clinical laboratory values [chemistry, hematology, urinalysis, coagulation laboratory tests, LBTs including aminotransferase (ALT and AST), GGT, ALP, and total and direct bilirubin levels] will be presented. For LBTs, 2-sided 95% CI of the mean for relative and absolute change from baseline 1 to each post-baseline visit and the last visit, and actual values at each visit will be presented along with descriptive statistics. Relative and absolute changes from baseline 1 to each post-baseline visit and the last visit will also be presented for quantitative variables. For clinical chemistry assessments and urinalysis tests with quantitative results, baseline 1 is defined as the average of all Screening results and results on the day of the planned single dose if both results are available. Otherwise, baseline 1 will be defined as the last non-missing assessment prior to the study drug administration of planned single dose. For other laboratory parameters, baseline 1 is defined as the last non-missing assessment of that parameter prior to the study drug administration of planned single dose. For categorical variables (i.e., normal or abnormal findings, or qualitative clinical laboratory tests), a table of categorical values over time will be presented. Results of quantitative clinical laboratory values will be categorized as low, normal, or high according to laboratory range specifications. Shifts from baseline 1 to each scheduled post-baseline time point will be presented to show the number and percentage of patients in each category by parameter.

Similar summary tables presenting relative and absolute change from baseline 2 to each post-baseline visit and the last visit for the 12-week treatment period will be presented for LBTs and chemistry and urinalysis laboratory quantitative variables for patients in the Safety Analysis Set who actively entered 12-Week treatment period. For the 12-week treatment period, similar shifts from baseline 2 summaries will be presented for chemistry laboratory parameters based on the

baseline 2 of 12-week treatment period for patients in the Safety Analysis Set who actively entered 12-Week treatment period. Baseline 2 for the 12-week treatment period is defined as the last non-missing value of the assessment prior to the 12-week treatment period (V3).

All laboratory data test results, laboratory toxicity and corresponding CTCAE grades will be included in data listings.

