5.5 Risk/Benefit Assessment

Risk assessment

A3907 has been administered to 56 healthy subjects in the FIH study (A3907-001). This study demonstrated that A3907 was well tolerated at a dose of up to CCI in the SAD study and CCI (capsule formulation) administered daily for CCI in healthy subjects in the MAD study. The potential risks to study participants associated with A3907 are described in the Guidance to Investigator section of the Investigator's Brochure. The most common A3907-related AEs in the FIH study were diarrhoea, abdominal pain, and headache.

Pharmacokinetic analysis revealed that A3907 was slowly absorbed (T_{max} approximately CCI c hours) and dose proportionality was demonstrated at single doses of CCI; a slightly less than dose proportional- increase was observed with multiple doses of CCI to CCI for 7 days. Repeat doses of A3907 resulted in CCI

in the SAD study, and [CCI] in the MAD study. Nonclinical secondary and safety pharmacology studies, general toxicity studies, and in vitro genotoxicity studies have also been conducted with no adverse effects of concern identified. Nonclinical toxicology studies of A3907 showed no signs of acute toxicity following single repeated oral dosing in rats and dogs up to a dose of [CCI] mg/kg/day and [CC] mg/kg/day, respectively, for up to 13 weeks. Elevated ALP and/or ALT values were observed at a dose of [CCI] mg/kg/day in the 7- and 14-day repeat dose studies in the dog; however, the elevations were fully or almost fully reversed at the end of the recovery phase. Elevations in liver enzymes were not observed in the 13-week dog study or the FIH study.

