7.2.2 Inclusion Criteria

Patients meeting all of the following criteria will be considered eligible for enrollment in the study:

Diagnosis and Criteria for Inclusion:

1. Adults between 18 and 75 years of age (inclusive).

2. Have a clinical diagnosis of large-duct PSC with evidence of more than 6 months duration with either a consistent MRCP or ERCP showing sclerosing cholangitis and historical evidence of elevated ALP.
3. Willing to sign informed consent.
4. Women of childbearing potential (WOCBP) and males with female partners of childbearing potential must agree to use contraception as detailed in [Section 9.3.18](#). Women of nonchildbearing potential (WONCBP) must meet the definition in [Section 9.3.18](#) and have a confirmatory FSH level ≥ 40 mIU/mL.
5. ALP value $> 1.5 \times \text{ULN}$ but $\leq 10 \times \text{ULN}$ at Visit 1 (Screening). Before starting 12 weeks treatment variability of $< 30\%$ between ALP values at Visit 1 and Visit 2 must be confirmed. If variability is $> 30\%$ a third ALP value may be obtained. If the third ALP value meets $> 1.5 \times \text{ULN}$ but $\leq 10 \times \text{ULN}$ the patient can start the 12-week treatment period.
6. Arms 1-3 Only: Total bilirubin $< 1.5 \times \text{ULN}$ (unless due to Gilberts Syndrome or hemolysis) and normal direct bilirubin.
7. AST and ALT $\leq 5 \times \text{ULN}$
8. Serum bile acid level $> \text{ULN}$
9. Arms 1 - 3 Only: An MRCP or equivalent imaging modality performed within 6 months before the Screening Period that is consistent with PSC without a CRS,
10. Arm 4 Only: An MRCP or equivalent imaging modality performed within 6 months before the Screening Period that is consistent with PSC with a CRS, or clinically relevant bile duct obstruction (see Inclusion # 12 for additional information).
11. Use of UDCA with a total daily dose ≤ 23 mg/kg/day, or bile acid-binding resins are permitted, with a minimum of 3 months of stable treatment prior to the Screening Period, and expected to remain on a stable dose through the 12-week treatment period; or a minimum of 3 months off UDCA prior to the Screening Period if UDCA was recently discontinued.

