10.2.2.5 Safety Analysis

Safety data will be analyzed using descriptive statistics and overall summaries of AEs, SAEs, ECG, vital signs, physical examinations, clinical laboratory tests (hematology, clinical chemistry, urinalysis, and coagulation), and concomitant medication. Analyses will be performed using the safety analysis set.

Summaries of AEs (coded according to Medical Dictionary for Regulatory Activities [MedDRA] system organ class and preferred term) will include:

- Overview of the incidence of all AEs (AEs, Drug-related AEs, AEs leading to study discontinuation),
- TEAEs by system organ class (SOC) and preferred term (TEAEs, Drug-related TEAEs, TEAEs leading to study discontinuation),
- Intensity/severity of TEAEs by SOC and preferred term,
- Drug-related TEAEs by SOC and preferred term,
- TEAEs leading to study discontinuation by SOC and preferred term, and
- Treatment-emergent SAEs by SOC and preferred term.

Summaries of TEAEs will be presented separately by the single dose (Day 0 to Day 13) and 12-week (Day 14 to Day 112) treatment periods.

Concomitant medication use during the Treatment Period will be summarised by Anatomical Therapeutic Chemical (ATC) class and World Health Organization (WHO) preferred name.

Summaries of vital signs and clinical safety laboratories will be presented. For each visit, the actual results, the change from baseline, and the number and percentage of patients with potentially clinically significant values observed post-baseline will be presented.

Data listings will be provided for each patient for all safety parameters.

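### The ALP shift table cannot show worsening: entry requires ALP above 1.5 x ULN, SAP 9.2 has a single High band, and no other laboratory table counts patients whose ALP rises

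*SAP*

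**What the plan says.** **Shift tables.** SAP 9.2 sets the categories: "Results of quantitative clinical laboratory values will be categorized as low, normal, or high according to laboratory range specifications". It continues: "Shifts from baseline 1 to each scheduled post-baseline time point will be presented". For the 12-week period, "similar shifts from baseline 2 summaries will be presented for chemistry laboratory parameters".

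**Entry.** Protocol 7.2.2, criterion 5, applies to all four arms and reads in part "ALP value $> 1.5 \times \text{ULN}$ but $\leq 10 \times \text{ULN}$ at Visit 1 (Screening". Visit 1 and Visit 2 values must then agree within 30% before the 12-week period. Failing that, a third value must again lie above 1.5 and at or below 10 x ULN.

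**Baselines.** Under SAP 4.4.1 and 9.2, chemistry baseline 1 is the mean of the screening and dosing-day results when both exist. Otherwise it is the last value before the single dose. Baseline 2 is the last value before the 12-week period.

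**Other laboratory displays.** SAP 9.2 gives relative and absolute change in the liver tests with 95% confidence intervals. On grades it says: "All laboratory data test results, laboratory toxicity and corresponding CTCAE grades will be included in data listings". SAP 9.2.1 plans a count of patients with an abnormal liver test, six eDISH plots, and individual graphs for selected patients.

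**The protocol's promise.** Protocol 10.2.2.5 says of vital signs and safety laboratories that, for each visit, "the number and percentage of patients with potentially clinically significant values observed post-baseline will be presented".

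**The concern.** A shift table is meant to show how many patients moved, and in which direction. With one band above ULN and an entry rule that puts ALP in that band, the table has cells for improvement and none for deterioration.

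Safety is the primary objective, and ALP is both a secondary endpoint and the enzyme used to select the population. Liver enzymes also appear in the nonclinical record. A sentence in Protocol 5.5 beginning "Elevated ALP and/or ALT values were observed at a dose of" describes a finding in the 7- and 14-day dog studies. The same section adds that the elevations fully or almost fully reversed and were not seen in the 13-week dog study or the first-in-human study, so this is a reason to look rather than a known signal.

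At stake is the balance of the categorical safety output. For ALP it could report benefit but not harm.

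**Working it through.** The plan states no figure to reproduce here, so the check asks which cells of the ALP shift table can be filled. Values are in multiples of ULN, assuming the same ULN at both visits.

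**Step 1. Lowest baseline 1 under the 30% rule.** Take Visit 1 (V1) at the entry limit of 1.5. The protocol does not say what the 30% is relative to, so three readings are tried. Baseline 1 = (V1 + V2)/2.

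| 30% relative to | Lowest V2 | Lowest baseline 1 |
|---|---|---|
| V1 | 1.5 x 0.70 = 1.05 | 1.275 |
| V2 | 1.5 / 1.30 = 1.15 | 1.33 |
| mean of the two | 1.5 x 0.85 / 1.15 = 1.11 | 1.30 |

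All exceed 1, so baseline 1 is High on every reading.

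**Step 2. What a Normal baseline 1 would need.** (V1 + V2)/2 <= 1 requires V2 <= 2 - V1. At V1 = 1.5 that is V2 <= 0.5, a fall of (1.5 - 0.5)/1.5 = 67% between visits. Once V1 is 2 or more it is impossible, since V2 would have to be zero or negative.

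**Step 3. Movement from High.** Rises of 2-, 3- and 5-fold from any High baseline stay High. Leaving High needs a fall of 1 - 1/baseline: 33% from 1.5, 50% from 2, 80% from 5 and 90% from 10. A 4-fold rise from 2 to 8 is High-to-High.

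**Step 4. Do other displays count worsening ALP?**
- *Abnormal-liver-test n (%), SAP 9.2.1:* criteria use ALT, AST, bilirubin, INR, LDH and CPK. ALP is absent.
- *eDISH plots, SAP 9.2.1:* ALT or AST against bilirubin. ALP is absent.
- *Individual graphs, SAP 9.2.1:* ALP is included, but only for patients who meet the DILI criteria or have hepatic-enzyme TEAEs.
- *CTCAE laboratory grades, SAP 9.2:* listed, not tabulated.
- *Change from baseline, SAP 9.2:* gives the size of change, not the number of patients who worsened.

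**Step 5. Illustration (assumed values).** In an arm of six, one patient rises 4-fold (+300%) and five fall by 20%.
- Mean = (300 - 5 x 20)/6 = +33%.
- SD = sqrt[(266.7² + 5 x 53.3²)/5] = 131%.
- 95% CI = 33 ± 2.571 x 131/sqrt(6), about -104% to +170%.
- Median -20%, minimum -20%, maximum +300%.
- Shift table: 0 of 6 worse.

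**The case against.** The strongest reply is that this is a 24-patient descriptive study in which little can hide. SAP section 4 includes minimum and maximum in every continuous summary, so the 4-fold rise above is printed as +300%. Full graded listings are planned. A clinically significant laboratory deterioration is an AE under Protocol 9.3.4.3 and is counted by preferred term and severity in SAP 9.1. All of this stands, so a reader who infers that an ALP rise would be masked or averaged away goes further than the documents allow. What remains is narrower: the maximum identifies one value per visit without counting patients, and the TEAE route depends on the investigator's judgement.

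Four other inferences are tempting but not supported:
- **That the SAP silently drops the protocol's count.** SAP section 11 declares that investigator-judged laboratory significance is unavailable and will not be presented. That matches the rating in Protocol 9.3.5. It does not clearly cover a count of potentially clinically significant values, for which the protocol gives no laboratory thresholds. The two texts need reconciling; this is not concealment.
- **That ALT, AST and bilirubin share the defect.** The ALT/AST entry limit of 5 x ULN is a ceiling, so patients may start normal. Arms 1-3 require normal direct bilirubin. SAP 9.2.1 already covers these tests, using multiples of baseline in eDISH where ALT or AST starts abnormal. For GGT there is no entry criterion, and Protocol 5.2.1 says only that it may be raised.
- **That unscheduled results are ignored.** SAP 4.5 accepts them within visit windows. What is missing is a worst-value row for laboratory shifts and a rule for several values in one window.
- **That literally every patient starts High.** The 30% rule is confirmed only before the 12-week period, after the single dose, and baseline 2 has no ALP floor of its own. The baseline 1 exception needs the 67% fall in step 2.

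**Conclusion.** The point holds for ALP. For essentially every patient, and for all who meet the 30% stability rule, baseline 1 is High, and the planned shift table can record only no change or improvement. No other laboratory table counts patients whose ALP worsened. This rests on the SAP's averaged chemistry baseline, a consistent reference range across the two visits, and a single category above ULN.

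The effect is a one-sided categorical display, not lost data. It alters neither the primary endpoint nor study conduct. The SAP itself supplies the remedy elsewhere: the vital-sign tables in 9.3 count values worse than an abnormal baseline and show shifts to the minimum and maximum. The change is worth making because it is cheap and lets the safety tables show harm as well as benefit.

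**What to change.** 1. **SAP 9.2, new table.** For ALP, and for GGT in patients whose baseline is above ULN, tabulate baseline against worst post-baseline value, scheduled plus unscheduled, by arm. Use either the CTCAE grade already derived for the listings or multiples of baseline. The sponsor should choose the bands, since the documents give none for ALP; they are display categories, not clinical action limits. State in a footnote which baseline is used and whether the grade is taken against ULN or baseline.
2. **Protocol 10.2.2.5 and SAP section 11.** Either present the number and percentage of patients with potentially clinically significant laboratory values, with the criteria written down, or state in section 11 that this count is withdrawn as well as the investigator's rating.
3. **Leave the rest.** The low/normal/high shifts can stay for other analytes, and the ALT, AST and bilirubin displays need not be replaced.

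The cost is SAP wording and one or two tables from data and grades already held, with no extra samples, visits or site work.
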